### **9.3.7 Technical complaints**

The investigator must assess whether a technical complaint is related to an AE.

The definitions, reporting process and timelines for reporting for technical complaints can be found in [Appendix 7](#).

### **9.3.8 Treatment of overdose**

In the event of an overdose, the investigator should closely monitor the patient for overdose-related AE/SAE and laboratory abnormalities and symptomatic medical treatment according to the clinical condition should be applied as relevant. Decisions regarding dose interruptions or modifications will be made by the investigator based on the clinical evaluation of the patient.

The overdose must be reported as medication error. Refer to Section [9.3.1](#) for further details.

For more information on overdose, also consult the current version of the concizumab IB.

### **9.3.9 Trial stopping rules**

If one of the below mentioned criteria is fulfilled, the Novo Nordisk Safety Committee will urgently evaluate all available data and decide on further actions:

- Significant thromboembolic event
- Event of DIC
- Event of TMA
- Death of trial patient which may be related to the trial product

If enrolment is put on temporary hold, relevant data will be submitted to regulatory authorities, according to local regulations, to support restart of enrolment.

## **9.4 Safety assessments**

Planned timepoints for all safety assessments are provided in the flowchart Section [2](#).

#### **9.4.1 Concomitant illness and Medical History**

A **concomitant illness** is any illness that is present at the start of the trial (i.e. at the first visit) or found as a result of a screening procedure or other trial procedures performed before exposure to trial product.

**Medical history** is a medical event that the patient has experienced in the past.

In case of an abnormal and clinically significant finding, the investigator must record the finding on the Medical History/Concomitant Illness form if it is present at screening. Any new finding fulfilling the AE definition (see [Appendix 5](#)) during the trial and any clinically significant worsening from baseline (visit 1/1a) must be reported as an AE (see Section [9.3](#)).

Recording of haemophilia arthropathy in medical history must be performed.

#### **9.4.2 Physical examinations**

The physical examination includes the following:

- General appearance
- Head, ears, eyes, nose, throat, neck
- Respiratory system
- Cardiovascular system
- Gastrointestinal system including mouth
- Genito-Urinary system
- Musculoskeletal system
- Central and peripheral nervous system
- Skin
- Lymph node palpation

Investigators should pay special attention to clinical signs related to previous serious illnesses.

The investigator must evaluate the results of the examination and record the outcome in the eCRF as:

- normal or abnormal.
- if abnormal the investigator must:
  - specify the abnormality
  - record if the result is clinically significant (Yes/No)
  - if observed before or at Screening: record as Medical History (Section [9.4](#))
  - if observed after screening: report an AE/SAE (Section [9.3](#)).

#### **9.4.3 Body measurements**

Body measurements will be assessed according to the flowchart in Section [2](#).

- Height (cm), at screening
- Body Weight (kg), with 1 decimal at all visits

The body weight assessed at each visit will be used for determination of the concizumab dose to be administered until next visit.

Measurements will be reported in the eCRF.

#### 9.4.4 Vital signs

- Oral, Rectal, Axillary, Ear or Skin temperature (°C), pulse rate (beats/min), respiratory rate, as well as diastolic and systolic blood pressure (mmHg) will be assessed as specified in the flowchart in Section [2](#).
- Blood pressure and pulse measurements or vital signs assessment should be preceded by at least 5 minutes of rest for the patient in a quiet setting without distractions (e.g. television, cell phones).
- Blood pressure at screening will consist of 3 diastolic and systolic blood pressure measurements with intervals of at least 1 minute. All three readings must be entered in the eCRF and the average of the 3 blood pressure readings will be recorded on or calculated in the eCRF. At the subsequent visits, the blood pressure should only be measured once.
- Blood pressure and pulse measurements will be assessed in sitting position, if applicable with a completely automated device. Manual techniques will be used only if an automated device is not available.

The investigator must evaluate the results and classify the outcome as either:

- Normal or abnormal
- If abnormal the investigator must:
  - Specify the abnormality
  - Record if the result is clinically significant (Yes/No)
  - If observed before or at screening: record as concomitant illness/Medical History (Section [9.4.1](#))
  - If observed after screening: report an AE/SAE (Section [9.3](#))

Measurements will be reported in the eCRF.

#### 9.4.5 Electrocardiogram (ECG)

For patients in arms 1, 2 and 4, an ECG must be taken according to flowchart [2](#). For patients in arm 3, the data collected in phase 2 will be reused.

The investigator must evaluate the ECG (standard 12 lead) at screening and classify the outcome as either:

- Normal or abnormal
- If abnormal the investigator must:
  - Specify the abnormality
  - Record if the result is clinically significant? (Yes/No)
  - If observed before or at Screening: record as concomitant illness/Medical History (Section [9.4.1](#))
  - If observed after screening: report an AE/SAE (Section [9.3](#))

The ECG results must be dated and signed by the investigator to verify that the data have been reviewed. Outcome will be reported in the eCRF.

#### 9.4.6 Clinical safety laboratory assessments

All protocol-required laboratory assessments, as defined in [Appendix 2](#) and [Appendix 3](#), must be conducted in accordance with the laboratory manual and the flowchart in Section [2](#). The laboratory will provide instructions on sampling, handling of samples, labelling and shipment of samples.

For the clinical safety laboratory assessments: Coagulation parameters, Haematology, Biochemistry and Urinalysis the investigator must evaluate the results and classify the outcome as either:

- Normal or abnormal
- If abnormal the investigator must:
  - Specify the abnormality
  - Record if the result is clinically significant (Yes/No)
  - If observed before or at screening: record as concomitant illness/Medical History (Section [9.4.1](#))
  - If observed after screening: report an AE/SAE ([Appendix 5](#))

For clinical safety laboratory assessments FVIII/FIX activity and FVIII/FIX inhibitors investigator will only evaluate the results according to inclusion/exclusion criteria.

Above mentioned measurements, except urinalysis, will be reported to the sites by the central laboratory on an ongoing basis.

If deemed relevant as per the investigator's discretion, Novo Nordisk may perform blood analyses for COVID-19 antibodies. These analyses will be performed at a special laboratory and will only be performed if back-up material from other samples are available. No additional blood sampling will be performed. The results from such tests will be reported directly to site(s) via Novo Nordisk.

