### **Events meeting the AE definition**

- Any abnormal laboratory test results or safety assessments, including those that worsen from baseline, considered clinically significant in the medical and scientific judgment of the investigator.
- A CLAE: a clinical abnormal laboratory finding which is clinically significant, i.e. an abnormality that suggests a disease and/or organ toxicity and is of a severity that requires active management. Active management includes active treatment or further investigations, for example change of medicine dose or more frequent follow-up due to the abnormality.
- Abuse: Persistent or sporadic, intentional excessive use of a medicinal product, which is accompanied by harmful physical or psychological effects (e.g. overdose with the intention to cause harm).
- Misuse: Situations where the medicinal product is intentionally and inappropriately used not in accordance with the protocol or the terms of the marketing authorisation.
- Exacerbation of a chronic or intermittent pre-existing condition including either an increase in frequency and/or intensity of the condition.
- Signs, symptoms or the clinical sequelae of a suspected drug-drug interaction.
- Signs, symptoms or the clinical sequelae of a suspected overdose of trial product regardless of intent.
- A "lack of efficacy" or "failure of expected pharmacological action" per se will not be reported as an AE or SAE. Such instances will be captured in the efficacy assessments. However, the signs, symptoms and/or clinical sequelae resulting from lack of efficacy will be reported as AE or SAE if they fulfil the definition.

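### Sections 9.4.2, 9.4.4 and 9.4.6 do not tie post-screening AE reporting to clinical significance or to new findings, as 9.4.1 and Appendix 5 do, so sites can apply different triggers

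*Protocol*

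**What the plan says.** Protocol Section 9.4.6 sets its scope as follows: "For the clinical safety laboratory assessments: Coagulation parameters, Haematology, Biochemistry and Urinalysis the investigator must evaluate the results". If a result is classified as abnormal, the investigator works through parallel bullets. He or she specifies the abnormality, records Yes or No for clinical significance, records it as concomitant illness or medical history if seen at or before screening, and otherwise: "If observed after screening: report an AE/SAE", followed by a pointer to Appendix 5. Section 9.4.4 uses the same list for vital signs. Section 9.4.2 uses it for physical examination: "if observed after screening: report an AE/SAE". Both point to Section 9.3.

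Section 9.4.1 is conditional throughout. At screening: "In case of an abnormal and clinically significant finding, the investigator must record the finding". During the trial, a new finding is reported if it fulfils the AE definition, and "any clinically significant worsening from baseline (visit 1/1a) must be reported as an AE".

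Appendix 5, under events meeting the AE definition, counts abnormal laboratory results and safety assessments when they are "considered clinically significant in the medical and scientific judgment of the investigator". It describes a clinical laboratory adverse event as "a clinical abnormal laboratory finding which is clinically significant" and severe enough to need active management. Pre-existing conditions, including those identified during screening, are listed as not meeting the definition.

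**The concern.** The bullets are triggered by the word abnormal. The Yes/No answer is collected but nothing in the list depends on it, and there is no condition that the finding be new or worse since screening. For a result that is abnormal but not clinically significant, a site following the bullet would report an AE, while a site following 9.4.1 and Appendix 5 would not.

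Safety is a stated secondary objective and the trial is open label. Section 5.1 of the 56-week SAP summarises AEs by number and percentage of subjects, number of events and rate. Section 5.6.2 adds severity, seriousness, relation to treatment and a table of AEs seen in at least 5% of subjects. All of these inherit whichever trigger the site used. If sites differ, part of the variation in AE rates is reporting habit.

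**Working it through.** **Wording, side by side**

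| Place | Trigger after screening | Depends on clinical significance? | Depends on new or worse? |
|---|---|---|---|
| 9.4.2, 9.4.4 | Abnormal (pointer to 9.3) | Not stated | Not stated |
| 9.4.6 | Abnormal (pointer to Appendix 5) | Not stated | Not stated |
| 9.4.1 | New finding meeting the AE definition, or worsening | Yes, for worsening; through the definition, for new findings | Yes |
| Appendix 5 | Abnormal result or assessment | Yes | Pre-existing conditions excluded |

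The triggers differ on their face. They agree only if the pointers are read as importing the Appendix 5 condition.

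**Size under the literal reading**

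The documents give no figure to reproduce. The inputs are:

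- Analytes, Table 18: haematology 9 (four named plus five differential counts), biochemistry 8, coagulation 8. 9 + 8 + 8 = 25. Urinalysis is screening only and is left out.
- Post-baseline laboratory visits to week 24, Section 2 flowchart: weeks 1, 4, 8, 12, 16, 20 and 24, so v = 7.
- Assumption: an analyte is out of range by chance with probability p = 2.5% or 5%. This is not in the documents.
- Assumption: m = 10 in place of 25, to allow for related analytes (PT with INR, leucocytes with the differential) amounting to one finding.

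Expected flags are m × p per visit and m × p × v by week 24. With independence, the chance of at least one is 1 − (1 − p)^m per visit and 1 − (1 − p)^(mv) by week 24.

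| m | p | Flags per visit | At least one per visit | Flags by week 24 | At least one by week 24 |
|---|---|---|---|---|---|
| 25 | 5% | 1.25 | 72.3% | 8.75 | over 99.9% |
| 25 | 2.5% | 0.625 | 46.9% | 4.4 | 98.8% |
| 10 | 5% | 0.50 | 40.1% | 3.5 | 97.2% |
| 10 | 2.5% | 0.25 | 22.4% | 1.75 | 83.0% |

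The range is therefore about 2 to 9 flags per patient.

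**Checks on the range**

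- Repeats: these counts treat a recurring deviation as a new flag each time. Counting each analyte once per patient, m × (1 − (1 − p)^v), gives 7.5 at the top (25 analytes, 5%) and 1.6 at the bottom (10 analytes, 2.5%). If the same patients were out of range at every visit, it would fall to the per-visit figures, 0.25 to 1.25.
- Total TFPI: Table 18 lists it under coagulation, but 9.4.6 calls it an exploratory biomarker. Without it, 24 × 0.05 × 7 = 8.4 and 24 × 0.025 × 7 = 4.2.
- Arm 1 may have the week 1 visit by phone. With 6 samples the ends become 25 × 0.05 × 6 = 7.5 and 10 × 0.025 × 6 = 1.5.
- The 5% table: one analyte would be flagged at least once by week 24 in 1 − 0.975^7 = 16.2% of patients at p = 2.5%, and in 1 − 0.95^7 = 30.2% at p = 5%. Both exceed 5% if visits are independent. With fully persistent deviations they return to 2.5% and 5%.

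Under the 9.4.1 and Appendix 5 rule, a chance deviation judged not clinically significant yields no AE.

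**The case against.** The best answer is that the bullets are shorthand. The 9.4.6 bullet ends by pointing to Appendix 5, and the other two point to Section 9.3, which concerns events that meet the AE definition and refers to Appendix 5 for it. The paired screening bullet is equally unconditional, yet the section it cites, 9.4.1, requires clinical significance. The Yes/No item would serve little purpose if every abnormality were reported. Appendix 2 has the investigator review laboratory results for AEs, which implies judgement. Even confirmed platelets or fibrinogen below the lower limit of normal lead, in 9.4.6, only to a recommendation to consider clinical evaluation. Abnormal is itself the investigator's classification and is not equated with out of range, so the arithmetic counts results and not reports.

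Much of this stands. A reader might infer that these sections order an AE for every abnormal value, in direct opposition to Appendix 5. The documents do not support that, because the pointers make a reconciling reading available and arguably the more natural one.

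What remains is that no bullet states the condition. Appendix 5 also contains the recording and reporting procedures, so its pointer can equally be read as saying how to report. Its general definition says an abnormal laboratory finding can be an AE. Two careful sites could defend different practice.

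**Conclusion.** This is a real drafting inconsistency, worth correcting, with a limited effect. The AE trigger in 9.4.2, 9.4.4 and 9.4.6 is left open where 9.4.1 and Appendix 5 make it conditional. If the bullets are followed literally, roughly 2 to 9 chance laboratory flags per patient could arise by week 24. That rests on the assumed 2.5% to 5% rate, on 10 to 25 separate analytes, on counting repeats, and on equating abnormal with out of range. Shifts caused by the disease or by TFPI inhibition are not included.

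Two further inferences should be resisted. Nothing in the documents shows that sites report this way, so the figures are not an estimate of inflation in this trial. Nor would the main safety signal be diluted: thromboembolic events are AESIs with their own definitions and their own count. The exposure is confined to the general AE tables, which are descriptive; the 56-week SAP tests no hypotheses, and the primary and key secondary tests use bleeds and SF-36v2 scores. Laboratory values are also summarised separately as change from baseline.

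**What to change.** In 9.4.2, 9.4.4 and 9.4.6, replace the last bullet with: *If observed after screening and the finding meets the AE definition in Appendix 5 (clinically significant, and new or worsened since screening): report an AE/SAE.* Put the same condition in the eCRF guidance. The same edit in 9.4.5 is for consistency only, because the ECG is done only at screening.

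The cost is one line in each section and a guidance update. No new data are needed, since clinical significance is already recorded, and no treatment rule changes. The edit works forward only; it does not reconcile events already reported under different readings.

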#### Concizumab ELISA (PK ELISA and ELISA IVD)

Concizumab will be quantified using a validated enzyme-linked immunosorbent assay (ELISA). Recombinant human TFPI will be used to capture concizumab. A colorimetric detection signal is obtained by the enzymatic reaction of horseradish peroxidase labelled anti-human IgG4 specific antibodies with the chromogenic substrate TMB (3,3',5,5'-tetramethylbenzidine). The amount of concizumab present in the calibration, quality control and test samples correlate with the obtained signal strength.

Validation of the assay has been performed following current bioanalytical guidelines for method validation. Additional assay validation of the concizumab ELISA IVD, specifically with regards to assay precision, has been performed to support the Investigational Device Exemption.

Plasma concizumab concentrations will be measured pre-dosing (trough) as specified in the flowchart in Section [2](#). Samples for assessment of concizumab trough values will be collected pre-dose to concizumab prophylaxis. Patients must be instructed to take their daily dose of concizumab after the blood sampling have taken place when visiting the site.

The sample taken at visit 4a (arm 2, 3, 4) and visit 9a.2 (arm 1) is to determine whether the dose should be adjusted. The sample is analysed using the concizumab ELISA IVD. These results (in ng/mL) will be communicated directly to the investigator by the central laboratory (see

Section [9.2.2](#)). All other samples will be analysed using the concizumab PK ELISA. The ELISA data will be reported in a bioanalytical report after the end of the trial at the latest.

## Safety laboratory data evaluation

In the event of confirmed central laboratory test results including one or more of below:

- platelets <LLN (central lab)
- fibrinogen < LLN (central lab)
- any other laboratory parameters of concern to the investigator

It is recommended that the investigator considers clinical evaluation of the patient and determine if further medical action is needed.

## Total TFPI

Total TFPI ELISA sampling will be performed according to the flowchart in Section [2](#).

The total TFPI level (free TFPI and concizumab bound TFPI) will be included as an exploratory biomarker assessment. The assay is a classic sandwich ELISA, where TFPI is captured via a polyclonal anti-TFPI antibody. This antibody binds to a region distant to the binding site of concizumab hence both, free TFPI and concizumab bound TFPI will be captured. Detection is done using a monoclonal antibody targeting TFPI. This antibody will not bind to the concizumab epitope of TFPI. Results will be reported in ng/mL TFPI.

### 9.4.7 Immunogenicity assessments

Samples for the determination of anti-drug antibodies will be collected according to the flowchart in Section [2](#). All patients will have samples drawn at V1/V1a, but only patients randomised/allocated to concizumab treatment (arms 2, 3 and 4) will have samples drawn at the remaining indicated timepoints in the main part of the trial. In the extension part of the trial, samples must be drawn for all patients (arms 1–4). Sampling should always take place prior to administration of concizumab. In case of suspected hypersensitivity reaction requiring systemic treatment, additional blood samples are to be collected; refer to Section [9.4.8](#).

Assessment of binding antibodies against concizumab (anti-drug antibodies (ADA) will be performed at specialised laboratories whereas assessment of neutralising antibodies will be performed at Novo Nordisk.

Analysis for ADA will be done with a bridging ECL assay (binding ADA assay) using labelled concizumab for antibody capture and detection. If a sample is confirmed positive in the confirmatory assay, the sample is considered positive for binding antibodies. Confirmed positive samples will be characterised in a specificity assay for binding to IgG backbone or the S241P mutation. Furthermore, positive samples will be characterised for neutralising activity using a neutralising ADA assay. All antibody assays are validated according to international guidelines and recommendations.

The following data will be available:

- Anti-concizumab antibodies
- Anti-concizumab antibody titres
- Anti-concizumab binding antibodies cross-reacting with IgG4 backbone or S241P mutation

- Anti-concizumab neutralising antibodies

The samples will be analysed and reported to sites at the primary analysis cut-off and at end of extension part (end of trial). A detailed description of the assay methods will be included in the antibody analysis report at the end of the trial.

Patients positive for binding antibodies at end of follow-up may be followed outside this protocol.

#### **9.4.8 Hypersensitivity reaction**

If suspicion of a hypersensitivity reaction occurs, patients should be instructed to contact the site staff as soon as possible for further guidance, see [Appendix 5](#).

In the event of a severe local and/or systemic hypersensitivity reaction possibly or probably related to trial product, blood sampling for assessment of anti-concizumab IgE antibodies as well as anti-concizumab antibodies should be conducted in relation to the reaction and no later than 1-2 weeks after the event. Additional testing may be performed locally if deemed relevant (e.g. anti-Host Cell Proteins (HCP) antibodies).

In the event of a severe systemic hypersensitivity reaction to trial product, it is recommended also to test for tryptase (total and/or mature tryptase) within 3 hours of the reaction. Moreover, a baseline tryptase measurement is necessary 1-2 weeks after the immediate severe hypersensitivity reaction due to individual variation in tryptase baseline concentration.

A follow up visit should be conducted 3-4 weeks post the allergic reaction with repeated blood sampling for assessment of anti-concizumab IgE antibodies as well as anti-concizumab antibodies and if possible also at a visit 3 month after the hypersensitivity reaction for assessing the persistence of the IgE response. Tryptase measurements are not required at the follow up visits.

Additionally, basophil activation testing may be performed if deemed relevant. This can be performed using existing samples and/or by analysing the patient's basophil cells from an additional blood sample taken 3-4 weeks and no later than 2 months after the event. Similarly, prick tests and/or intra-dermal tests may be performed if relevant using trial product or components of trial product. Complement may be measured in case of suspicion of immune complex mediated hypersensitivity reactions.

The following additional tests can be performed locally or at special laboratories if deemed relevant:

- Anti-concizumab IgE antibodies
- Anti-concizumab antibodies (additional to scheduled time points)
- Anti-Host Cell Proteins (HCP) antibodies
- Anti-HCP IgE antibodies
- Basophil activation results
- Prick test/intra-dermal test
- Complement test results
- Tryptase (total and/or mature tryptase)

In case laboratory samples for severe hypersensitivity reactions are analysed at special laboratories, the results from the analysis will be reported directly to site(s) via Novo Nordisk.

Hypersensitivity reactions including test results should be reported as an AE requiring additional data collection, see Section [9.3.1](#)

